patients with unstable heart disease (i.e., unstable angina or AMI in the past 4 weeks) per the medical contraindications for NRT. Some participants may experience nausea, jitteriness, insomnia, and vivid dreams. To address these concerns, participants will receive written information and information from their counselor about how to manage any of these symptoms. They will be given advice on when they might need to reduce their nicotine dose (whether through decreasing smoking or decreasing NRT). Discontinuation of NRT may be recommended for participants whose symptoms cannot be otherwise controlled through a dose reduction and/or decreasing smoking. We will track adverse events during regularly scheduled study visits and through spontaneous reports made by participants. [name] and [name] will be made aware of unexpected or serious AEs within 24 hours of the first report by participants; all other AEs will be reviewed weekly by [name] and discussed at regular meetings with [name]. SAEs will be reported to the KUMC HSC and to the FDA with 24 hours of first awareness of the event. Unexpected adverse events that are related to the study medication will be reported to KUMC HSC and to the FDA within 5 working days of first awareness of the event if the event is not serious fatal and within 24 hours of first awareness if the event is serious. Unexpected adverse events that are unrelated to the study medication will be reported to the KUMC HSC during yearly routine event reporting. [name] will determine relatedness for each reported AE. SAEs will be defined as any event experienced by a study subject while on the study medication that is fatal, life-threatening (subject was at risk of death from the event as it occurred), disabling or incapacitating, requires inpatient hospitalization or prolongs a current hospitalization, is a congenital anomaly in the offspring of a subject who received the study medication, or required intervention to prevent permanent impairment or damage.

III. SUBJECT PARTICIPATION

A. Recruitment

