To date, no studies have explored treatment options for non-daily smokers and, as a result, treatment guidelines are not available to guide patients or healthcare providers. The study will compare two treatments -- smoking cessation counseling alone versus counseling in combination with patients' choice of nicotine patch, gum, or lozenge -- on their effects on quitting smoking and reducing exposure to nicotine and cancer causing agents. Findings will identify which patients are most likely to benefit from each form of treatment (counseling, nicotine gum, patch, or lozenge) and will allow patients and providers to estimate their chances of success based on personal characteristics – for example, age, gender, level of smoking – and the treatment they chose. This study will determine if NRT is safe and effective for AA non-daily smokers. The program will be the first to examine treatment options for non-daily smokers and could directly contribute to the first evidence-based guidelines for treating the 9.7 million U.S. adult non-daily smokers for whom no guidelines currently exist.

[figure not shown]
II. RESEARCH PLAN AND DESIGN

A. Study Objectives

The objective of this study is to examine if NRT is an effective treatment option for AA non-daily smokers. Outcomes will be measured at weeks 12 and 26 and will include biologically confirmed smoking abstinence, nicotine intake, carcinogen exposure, days abstinent, NRT adherence and side effects.

B. Study Type and Design:

The proposed study is a randomized trial of 384 AA non-daily smokers randomized to receive either 5 sessions of smoking

Projected sample size by group using 2:1 randomization, whereby 67% are randomized to C+NRT and 33% are randomized to C

cessation counseling in combination with 12 weeks of nicotine patch, gum, or lozenge (C+NRT) or 5 sessions of smoking cessation counseling alone (C). We will use 2:1 randomization; for every patient randomized to C, two will be randomized to C+NRT (see Figure). The primary outcome is biologically-confirmed 7-day abstinence from smoking at 12 weeks. Patient- and provider-driven secondary outcomes include reductions in nicotine intake and carcinogen exposure, days abstinent, NRT adherence and side effects. Participants will be recruited from the University of Kansas Medical Center (KUMC) and Swope Health Central, a community-based primary care clinic in urban Kansas City that serves a predominately AA clientele.

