C. Sample size, statistical methods, and power calculation

384 AA non-daily smokers will be randomized. We will use 2:1 randomization; for every patient randomized to C, two will be randomized to C+NRT (see Figure). Randomization will be determined by computer-generated random numbers generated by [name]. Randomization assignments will be placed in sealed envelopes by a member of [name] team with sequential study ID numbers. After baseline data collection has been completed, the research assistant will select the sequential study ID number from the sealed envelope to determine the randomization assignment.

The maximum number of participants enrolled in C will be 128 and the maximum number enrolled in C+NRT will be 256. Our sample size is based on our primary outcome, biochemically confirmed point-prevalence abstinence at Week 12 using an intent-to-treat approach. Based on treatment studies with AA light smokers who have received tobacco treatment guideline-based counseling and no pharmacotherapy, we expect a 10% point prevalence abstinence rate in the C group and a 20-25% point prevalence abstinence rate in the C+NRT group based on recent meta-analyses and studies examining the effectiveness of these medications in AA light smokers.^{11,28,45,46} Using the chi-square test, along with the assumptions above, 256 participants in the C+NRT group and 128 participants in the C group (n=384), we will have 95% power to detect an increase from 10% to 25% in cessation at Week 12 between C and C+NRT, 87% power to detect a and increase from 10% to 22.5%, and 71% power to detect an increase from 10% to 20% with a type 1 error rate of 5%.

Analysis Plan for Each Aim

All primary analyses on smoking cessation will be conducted using intent-to-treat and will code those lost to follow-up as smokers. Subsequently we will evaluate the missing data pattern. If there is a differential loss based upon group, multiple imputation techniques will also be used.

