Specific Aim 2: To compare patient- and provider-desired outcomes -- e.g., nicotine intake, carcinogen exposure, number of days abstinent, and side effects – among AA non-daily smokers receiving C versus C+NRT and, within the C+NRT group, examine the choice of NRT and use during the treatment period. Hypothesis: Participants randomized to C+NRT will demonstrate significantly greater reductions in nicotine intake and carcinogen exposure and significantly more days abstinent, while experiencing no differences in side effects as participants randomized to C. Analytic strategy: We will utilize linear mixed models to longitudinally (week 12 and 26) compare nicotine and carcinogen exposure between the two groups, then subsequently examine the effects of the covariates listed in the measurement table above using a best subsets selection method for both nicotine and carcinogen exposure independently. A generalized linear mixed model approach will be used to model days abstinent, controlling for number of days in study, to assess the effect of treatment on this endpoint and best subsets selection will be used to examine the effects of covariates on this endpoint. For each of these models, based upon the sample size, we anticipate that ten to twelve covariates could be included in a final model. We will compare the prevalence of any side effect as well as each specific side effect, from baseline to week 12, between the two groups using the chi-square test. If there is a global difference we will examine, within the NRT group, if type of NRT impacts the side effect profile. Within the NRT group we will descriptively summarize the number and percent of subjects who choose each type of NRT. Subsequently we will describe and descriptively compare the percent of subjects within each of these subgroups who use the NRT of choice during the treatment period (i.e., percent of patients within the patch, gum, and lozenge groups who used the medication).

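### The SAE definition covers only time on study medication, so SAE classification and the automatic 24-hour report leave out the counseling arm and nearly all time after NRT stops

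*Combined protocol and SAP*

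**What the plan says.** The definition stands in the adverse-event text just before Section III (Subject Participation): "SAEs will be defined as any event experienced by a study subject while on the study medication that is fatal". The sentence goes on to life-threatening events, disability, hospitalization, congenital anomaly, and intervention needed to prevent lasting damage. The limit to time on medication comes before the list and governs all of it. One criterion is worded differently, since it applies when the event "is a congenital anomaly in the offspring of a subject who received the study medication".

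The same text sets the reporting routes. SAEs go to the HSC and the FDA within 24 hours. Unexpected events related to the medication go to both within 5 working days, or within 24 hours if serious. Unexpected events unrelated to the medication go to the HSC once a year.

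Tracking of adverse events in general is not limited by arm or by medication status: "We will track adverse events during regularly scheduled study visits and through spontaneous reports made by participants".

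Section II.B gives NRT for 12 weeks to C+NRT and counseling alone to C. On size, Section II.C says: "The maximum number of participants enrolled in C will be 128 and the maximum number enrolled in C+NRT will be 256". On follow-up, Section II.A says: "Outcomes will be measured at weeks 12 and 26". Section I.C (Rationale) makes the safety claim: "This study will determine if NRT is safe and effective for AA non-daily smokers".

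**The concern.** Whether an event is called an SAE depends here on exposure as well as on seriousness. A participant in C is never on study medication, so no event in that arm can meet the definition. A participant in C+NRT leaves the definition when NRT ends. That may be early, because the same text foresees that stopping NRT may be recommended when symptoms cannot otherwise be controlled.

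Two things are at stake. First, the same hospitalization is reported within 24 hours in one participant and, at best, yearly in another, because of arm or timing alone. Second, a tabulation of SAEs under this definition would show zero in C by construction. A count in C+NRT would then have no control rate beside it, in a trial whose Rationale promises an answer on safety.

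**Working it through.** The plan gives no figure on this point, so the check has two parts: the reporting routes set side by side, and a count of person-time.

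**Routes for one event, for example a hospitalization**

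| Participant | SAE as defined? | External report under this text |
|---|---|---|
| C+NRT, taking NRT | Yes | HSC and FDA within 24 hours |
| C+NRT, NRT stopped; unexpected and judged related | No | HSC and FDA within 5 working days, or 24 hours if serious |
| C+NRT, NRT stopped; unexpected and unrelated | No | HSC, yearly |
| C; unexpected (unrelated, as no study medication is given) | No | HSC, yearly |
| Either arm, not on NRT; expected | No | None stated here |

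In the second row, the 24-hour limit applies if 'serious' has its ordinary meaning. If it refers back to the SAE definition, the limit is 5 working days.

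**Person-time inside the definition**

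Inputs: 128 in C and 256 in C+NRT (II.C); 12 weeks of NRT (II.B); follow-up to Week 26 (II.A); an NRT trial period of 3 to 9 days before the 12-week supply (II.E, NRT). Full enrollment, full follow-up and full NRT use are assumed.

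- C: 128 × 26 = 3,328 person-weeks, of which 0 are inside the definition.
- C+NRT: 256 × 26 = 6,656 person-weeks.
- Trial total: 3,328 + 6,656 = 9,984 person-weeks.
- Inside, 12 weeks only: 256 × 12 = 3,072. This is 3,072 / 6,656 = 46.2% of C+NRT and 3,072 / 9,984 = 30.8% of the trial. Outside: 69.2%.
- Inside, with a 9-day trial period added: 256 × (12 + 9/7) = 3,401. This is 51.1% of C+NRT and 34.1% of the trial. Outside: 65.9%.

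NRT stopped early, or never used, makes the share outside larger. With the definition extended to all randomized participants through Week 26, all 9,984 person-weeks would be inside.

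**The case against.** The definition sets a label and a reporting clock. It does not decide whether an event is recorded. A reader might infer that serious events are recorded in one arm only, or that safety capture as a whole differs by arm. The documents do not support either reading:

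- Adverse events are tracked for participants in general. Relatedness is determined for each reported event, and unexpected ones reach study leadership within 24 hours.
- Section II.F foresees one adverse event, feeling pressured to take part, under risks that apply to both arms.
- The side-effect measure (Weeks 4, 8 and 12) carries no arm restriction, whereas NRT adherence is marked for C+NRT only.
- The planned between-arm comparison under Aim 2 concerns those symptoms and not SAEs, so no stated analysis is damaged.

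Nor are all late events lost from expedited reporting. The rule for unexpected, medication-related events has no time-on-medication limit of its own, and the congenital-anomaly wording may reach past dosing.

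The word 'safe' appears in the Rationale, while the objective in II.A is framed around effectiveness, with side effects among the outcomes. Some text preceding the adverse-event section was not available to this review, so the wider monitoring plan cannot be judged.

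All of this stands, and it limits the consequence. It does not change the definition, which is a complete sentence. General tracking might allow serious events in C to be reconstructed from adverse-event records, but the text does not say that the records will be detailed enough. The symptom list (irritability, rash, nausea and the like, to Week 12) does not stand in for deaths and hospitalizations to Week 26.

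**Conclusion.** The point holds for SAE classification and for the automatic 24-hour report. Both exclude all of C and nearly all time after NRT stops, with a possible exception for congenital anomalies. The excluded share is about 66% to 69% of planned person-weeks to Week 26, depending on whether a trial period of up to 9 days is counted, and assuming full follow-up and 12 full weeks of NRT. This share measures time outside the SAE label. It is not unmonitored time and not an estimate of missed events, since the documents give no SAE rate.

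SAE counts as defined cannot be compared between arms, so they cannot support the Rationale's claim about safety. No planned endpoint or test is affected. The text should be changed because the defect is plain and the repair is small.

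**What to change.** Define an SAE as any event meeting one of the listed seriousness criteria in any randomized participant, in either arm, from enrollment to Week 26, whether or not NRT is being taken. Record NRT status at onset (on, stopped, never assigned) and relatedness as separate fields. Bring the congenital-anomaly wording into line with the same scope. State that SAEs will be tabulated by randomized arm, with on-NRT events shown separately within C+NRT.

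The cost is a revised definition, one sentence on tabulation, and slightly more reporting for C and for the follow-up period. No new visits are needed, because adverse events are already tracked at scheduled visits and by spontaneous report.

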Consent will be obtained prior to participant involvement. Individuals interested in the proposed study will meet the research assistant at Swope or the CRU. Each individual will be given a copy of the consent form and as much time as they need to review its contents. After the consent form is read, both the individual and the research assistant will review the consent form together and the potential participant will be encouraged to ask questions. Each individual will be reminded that participation in the study is completely voluntary and their decision to participate will not affect their current or future medical care at the treating facility. The consenting process will take place in a private location.

D. Alternatives to Participation

Alternatives to participating in the study are to quit "cold turkey" (without assistance), use other smoking cessation programs, purchase other NRT from their pharmacy, obtain a prescription for varenicline, bupropion or other smoking cessation products from their physician, or continue to smoke.

E. Costs to Subjects

There are no costs to subjects. All tests, procedures, and visits are being performed solely for research purposes and are not billable to insurance companies.

F. How new information will be conveyed to the study subject and how it will be documented

We have plans to publish data from this study in aggregate but will not provide any individualized feedback to participants.

G. Payment, including a prorated plan for payment

Participants will be given a \$40 electronically loaded gift card at Wks 0, 12 and a \$20 electronically loaded gift card at Wks 1, 4, 8, 10, 26 in appreciation for their time and participation. Participants must complete the visit to receive the reimbursement associated with that time point. Travel costs will not be reimbursed. Participants will also be given \$20 for each referral who is eligible and enrolls in the study. Each participant may refer up to 3 total referrals.

H. Payment for a research-related injury

Not applicable

IV. DATA COLLECTION AND PROTECTION

A. Data Management and Security

Confidentiality will be maintained by assigning each participant a study identification number and numerically coding all data. The association of the ID-code and the participant's name will be kept by [name] in a locked file cabinet. The screening questionnaire and all survey data will be directly entered into RedCap or CRIS and accessible only by study staff. Any paper copies of records will be kept in a locked filing cabinet in offices that are kept locked when unoccupied. Only summaries of group data will be reported in any publications or presentations, with no identification of individuals. Because identifiable information will be collected, participant privacy will be maintained throughout the duration of the study by adhering to the regulations set forth by the HIPAA Privacy Rule. More specifically, identifiable information will not be released without written authorization of the participant.

Mobile devices will not be used for data collection or storage. Identifiable data will not be sent outside of KUMC.

B. Sample / Specimen Collection

No more than 30 ml of urine will be collected at Weeks 0, 12, and 26. Urine will be de-identified, labeled with a study identification number, and stored at the Bioanalytical Laboratory at the Fairway Clinical Research Center under the direction of [name]. Samples will be accessible only to members the study team. Results from biomarker analyses will be de-identified and shared only with members of the research team. Any resulting publications will present the data in aggregate; individual participants will not be identified. Samples will be disposed of one month after the final report is sent out to the Principal Investigator, unless participants agree to have their urine stored for future testing. For participants who agree to future testing, samples of their urine will be stored indefinitely.

C. Tissue Banking Considerations

For participants who agree to future testing, samples of their urine will be stored indefinitely. New markers of nicotine and carcinogen exposure are being discovered and the stored urine samples would be used for analysis of these new markers. All samples stored for future biomarker analyses will be de-identified and accessible only to members of the study team. Results from these analyses will be de-identified and shared only with members of the research team. Any resulting publications will present the data in aggregate; individual participants will not be identified.

D. Procedures to protect subject confidentiality

Confidentiality will be maintained by assigning each participant a study identification number and numerically coding all data. All urine samples and survey data will be labeled with the study identification number and never with the participants name or other identifiable information. The association of the ID-code and the participant's name will be kept by [name] in a locked file cabinet and will only be accessible to members of the study team.

E. Quality Assurance / Monitoring

All data will be directly entered into our electronic data capture system (i.e., RedCap or CRIS) that contains edit checks to control the quality and completeness of data entry. Completeness of data entry will be automatically verified before each assessment is completed. The electronic data capture system is behind the KUMC secure firewall with role-based access that is HIPAA and human subjects compliant. There are no plans for ongoing third party monitoring.

V. DATA ANALYSIS AND REPORTING

A. Statistical and Data Analysis

See II.C. above (Sample Size, Statistical Methods, and Power Calculations)

B. Outcome

See II.C. above (Sample Size, Statistical Methods, and Power Calculations)

C. Study results to participants

Study results will not be shared with participants.

D. Publication Plan

We plan to publish results in appropriate tobacco journals – e.g., JAMA, JNCI, Journal of General Internal Medicine, Addiction, Annals of Behavioral Medicine, Nicotine & Tobacco Research, Cancer Epidemiology, Biomarkers, & Prevention.

E. Bibliography / References / Literature Cited

1. Centers for Disease Control and Prevention. Smoking-attributable mortality, years of potential life lost, and productivity losses--United States, 2000-2004. *MMWR Morb Mortal Wkly Rep.* Nov 14 2008;57(45):1226-1228.
4. Centers for Disease Control and Prevention. *Tobacco Control State Highlights, 2010.* Atlanta: U.S. Department of Health and Human Services, Centers for Disease Control and Prevention, National Center for Chronic Disease Prevention and Health Promotion, Office on Smoking and Health;2010.

APPENDIX I: VULNERABLE POPULATIONS

Not applicable
